10.2 Randomisation

10.2.1 Allocation- sequence generation

Balanced, permuted block randomisation (in a 1:1: ratio for the two study arms) will be performed online in Viedoc and stratified by centre.

10.2.2 Allocation- procedure to randomise a patient

We will use a computerised randomisation procedure for treatment allocation. Random treatment allocation will be executed on the online, password-protected platform designed for study purposes (Viedoc[™]) once eligibility has been confirmed and the informed consent has been signed.

10.2.3 Blinding and emergency un-blinding

The study participants (patients) and all study personnel, including investigators, personnel assessing outcomes, study nurses, data analysts and treating physicians and nurses, will be blinded to study drug allocation.

Un-blinding will be performed in the event of AEs where knowledge of the type of drug might be of importance to the personnel treating the patients, and in the event of SUSARS. Un-blinding will be performed by personnel with the designated role of performing unblinding, and the result will immediately be reported to the primary investigator, who will then take the required action(s). The eCRF is designed to handle emergency unblinding by allowing investigators to take on different roles, one of which is the role of emergency unblinder. When taking on this role, the investigator can unmask study drug assignment for a particular patient without further compromising the integrity of the randomisation list. Emergency unblinding is traceable in the eCRF system and will only be performed if requested by an investigator, and only if required to make important medical decisions for the patient in question. Two of the study personnel at the sponsor site only, will be given the emergency unblinding role. Their telephone numbers will be distributed among the study personnel. At least one of the designated emergency unblinders will be available at any time on a 24-hour basis. Unless unavoidable, other investigators and the personnel assessing outcomes, should not be made aware of treatment allocation.

10.3 Population for Analysis

The following populations will be considered for the analyses:

- Intention to treat (ITT) population: All randomised participants, regardless of protocol adherence.
- Safety population: All patients who have been enrolled in the trial, and who have received at least one dose of the investigational medicinal product (evolocumab or placebo).
- Per-protocol population (PP): Includes all subjects who have completed 12 months of treatment.

10.4 Planned analyses

The main statistical analysis is planned when the last patient has completed the end-oftreatment visit 12 months after randomisation. The number severity of adverse events will be assessed consecutively.

Deviation from the original statistical plan will be described and justified in the Clinical Study Report. Amendments to plan can be done until the day of database lock.

10.5 Statistical analysis

All statistical tests will be performed using a two-sided 5 % level of significance. Continuous efficacy variables will be analysed using baseline-adjusted ANCOVA for comparisons between the treatment arms. If necessary, values will be log-transformed to meet the assumptions of the tests. All analyses will primarily be analysed according to the intention-to-treat principle. The number of major clinical events will be analysed using descriptive statistics. Between-group differences in ordinal categorical variables, such as NYHA class, will be analysed using ordinal logistic regression, whereas the count variables will be assessed by Poisson regression. Demographic, efficacy and safety data will be summarised by treatment group using means, minimums, medians, maximums, interquartile ranges and standard deviations for continuous variables and frequency counts and percentages for categorical variables. Per protocol analyses will be performed using the same methods as for the intention-to-treat analyses.

The primary endpoint, the between-group difference in the baseline-adjusted intima thickness at 12 months, will be calculated by baseline-adjusted ANCOVA according to the intention-to-treat principle, the statistical null-hypothesis being that the intima thickness does not differ between the two treatment arms. Secondary analyses will be made according to the per-protocol-principle as baseline-adjusted absolute values after end-of-treatment.

Key, secondary endpoints:

The secondary endpoints "Percent atheroma volume as measured by IVUS" and "Cardiac allograft vasculopathy" will be tested, at a two-sided alpha level of 0.05, in a hierarchical fashion. The baseline-adjusted between-group difference in the atheroma volume, eGFR, quality of life, and biomarkers reflecting cardiac function, blood lipids, and inflammation will be calculated by ANCOVA according to the intention to treat principle. The statistical null-hypotheses are that the changes in these characteristics do not differ between patients allocated to evolocumab and patients allocated to placebo.

Secondary per protocol analyses will be performed using the same methods as for the intentionto-treat analyses. Exploratory analyses will be made for efficacy variables stratified by centre.

Safety analyses will include tabulation of type and frequency of all adverse events. Any serious adverse events will be reported with comprehensive narratives. Any value of safety laboratory parameters outside normal ranges will be identified.

Missing data will be omitted from analyses, i.e. there will be no imputation or estimation of missing values. However, a comparison of the baseline characteristics of those with an intima thickness measurement at 12 months and the baseline characteristics of those without a value will be performed to assess any bias introduced due to missing data. Statistical analyses will be performed in IBM SPSS Statistics version 21 or later.

11 Study management

11.1 Investigator delegation procedure

The principal investigator is responsible for making and updating a "delegation of tasks" listing all the involved co-workers and their role in the project. He will ensure that appropriate training relevant to the study is given to all of these staff, and that any new information of relevance to the performance of this study is forwarded to the staff involved.

11.2 Protocol adherence

Investigators ascertain they will apply due diligence to avoid protocol deviations. All significant protocol deviations will be recorded and reported in the Clinical Study Report (CSR).

11.3 Study amendments

If it is necessary for the study protocol to be amended, the amendment and/or a new version of the study protocol (Amended Protocol) must be notified to and approved by the Competent Authority and the Ethics Committee according to EU and national regulations.

11.4 Audit and inspections

Authorised representatives of a Competent Authority and Ethics Committee may visit the centre to perform inspections, including source data verification. Likewise, the representatives from sponsor may visit the centre to perform an audit. The purpose of an audit or inspection is to systematically and independently examine all study-related activities and documents to determine whether these

activities were conducted, and data were recorded, analysed, and accurately reported according to the protocol, Good Clinical Practice (ICH/GCP), and any applicable regulatory requirements. The principal investigator will ensure that the inspectors and auditors will be provided with access to source data/documents.

12 Ethical and regulatory requirements

The study will be conducted in accordance with ethical principles that have their origin in the Declaration of Helsinki and are consistent with ICH/GCP and applicable regulatory requirements. Registration of patient data will be carried out in accordance with national personal data laws.

12.1 Ethics committee approval

The study protocol, including the patient information and informed consent form to be used, must be approved by the regional ethics committee in each participating country before enrolment begins in the particular country.

The investigator is responsible for informing the regional ethics committee of any serious and unexpected adverse events and/or major amendments to the protocol as per national requirements.

12.2 Other regulatory approvals

The protocol will be submitted and approved by the applicable, national competent authorities before commencement of the study. The protocol will also be registered on www.clinicaltrials.gov before inclusion of the first patient.

12.3 Informed consent procedure

The investigator is responsible for giving the patients full and adequate verbal and written information about the nature, purpose, and potential risks and benefits of the study. Study participants will be informed as to the strict confidentiality of their patient data, but that their medical records may be reviewed for trial purposes by authorised individuals other than their treating physician.

It will be emphasised that study participation is voluntary and that the patient is allowed to refuse further participation in the protocol whenever she/he wants. This will not prejudice the patient's subsequent care. Written informed consent must be obtained for all study participants before enrolment in the study. This will be done in accordance with the national and local regulatory requirements. The investigator is responsible for obtaining signed informed consent.

A copy of the patient information and consent form will be given to the patients. The signed and dated consent forms will be filed in the Investigator Site File binder.

12.4 Subject identification

The investigator is responsible for keeping a list of all patients (who have received study treatment or undergone any study specific procedure) including patient's date of birth and personal number, full names and last known addresses.

The patients will be identified in the eCRFs by a study-specific, unique identification number.

13 Trial sponsorship and financing

The EVOLVD trial is an investigator-sponsored (ISS) study which receives funding from Amgen[®]. Amgen has also provided the study drug. The funding sources have had no role in the design of the study; neither will they participate in the implementation of the trial, in the analyses of the results, or

in the decision to publish. The investigators take sole responsibility for the integrity of the data, the writing of the manuscript and the dissemination of the results.

14 Trial insurance

The Principal investigator has insurance coverage for this study through membership of the Drug Liability Association.

15 Publication policy

Upon study completion and finalisation of the study report the results of this study will either be submitted for publication and/or posted in a publicly assessable database of clinical study results. We will allow for a separate publication of baseline characteristics once all subjects have been enrolled.

The results of this study will also be submitted to the Competent Authorities and the Regional Ethics Committees according to EU and national regulations. All personnel who have contributed significantly with the planning and performance of the study (Vancouver convention 1988) may be included in the list of authors. The funding sources have had no role in the conception of the study; neither will they participate in the implementation of the trial, in the analyses of the results, or in the decision to publish.

16 References

References

AE	Adverse event		
eCRF	Electronic Case report form		
CAV	Cardiac allograft vasculopathy		
CI	Confidence interval		
CRP	C-reactive protein		
DSMB	Data safety monitoring board		
EQ-5D-3L	EuroQoL five dimensions three levels [Questionnaire]		
EQ VAS	EuroQoL visual analogue scale		
EVOLVD	Cholesterol lowering with EVOLocumab to prevent cardiac		
	allograft Vasculopathy in De-novo heart transplant		
	recipients		
FAS	Full analysis set		
GCP	Good clinical practice		
ICH	International Conference on Harmonisation		
KCCQSS	Kansas City Cardiomyopathy Questionnaire		
NT-proBNP	N-terminal pro-B-type natriuretic peptide		
PCSK9	Proprotein convertase subtilisin–kexin type 9		
PPS	Per protocol set		
SAE	Serious adverse event		
SD	Standard deviation		
SF-36	Short form 36 [Questionnaire]		
SS	Safety set		
SUSAR	Suspected unexpected serious adverse reaction		
TAVI	Transcatheter aortic valve implantation		
TnT	Cardiac troponin T		

5 Introduction

5.1 Preface

Cardiac allograft vasculopathy (CAV) is characterised by diffuse thickening of the arterial intima. It is partly thought to be caused by atheromatosis. Statins reduce the incidence of CAV and improve survival in heart transplant recipients. However, despite the use of statins, CAV is prevalent and remains the leading cause of death in long-term survivors of heart transplant. Inhibitors of proprotein convertase subtilisin—kexin type 9 (PCSK9) substantially reduce cholesterol levels but have not been tested in heart transplant recipients.

The Cholesterol lowering with EVOLocumab to prevent cardiac allograft Vasculopathy in De-novo heart transplant recipients (EVOLVD) trial is a Nordic, multicentre, parallel group, randomized, double-blind placebo-controlled trial designed to assess the effect of the PCSK9-inhibitor evolocumab, in addition to standard care, on coronary intima thickness in patients who have recently received a heart transplant.

5.2 Purpose of the analyses

The purpose of the analyses laid out in this analysis plan is to evaluate the efficacy and safety of the PCSK9-inhibitor evolocumab in *de novo* heart transplant recipients.

6 Study Objectives and Endpoints

6.1 Study Objectives

The main objective of this study is to evaluate the effect of the PCSK9 inhibitor Evolocumab vs placebo on cardiac allograft vasculopathy in *de novo* heart transplant recipients.

Secondary objectives are to assess the impact of treatment on: i) cholesterol levels, ii) renal function, iii) cardiac function as assessed by biomarkers and echocardiography, iv) the number of rejections, and (v) safety and tolerability.

Exploratory objectives are to assess the effect of treatment on clinical events, defined as death, myocardial infarction, cerebral stroke, cancer, and end stage renal disease.

Additional objectives that will be explored in later substudies include – but are not limited to – the impact of treatment on (i) inflammation, (ii) HDL and total cholesterol, and (iii) quality of life.

6.2 Endpoints

In Sections 5.2.1 - 5.2.3, we present the endpoints that will be reported in the main publication of EVOLVD. Section 5.2.4 note some endpoints that will be reported in later substudies.

6.2.1 Primary endpoint

The primary endpoint of the EVOLVD trial is the baseline-adjusted maximal intimal thickness as measured by coronary intravascular ultrasound at 12 months' follow-up. The maximal intima thickness is defined as the largest distance (in mm) from the intimal leading edge to the external elastic membrane.

6.2.2 Secondary endpoints

- 1. Percent atheroma volume as measured by intracoronary ultrasound
- 2. LDL cholesterol
- 3. Estimated glomerular filtration rate
- 4. N-terminal pro-B-type natriuretic peptide
- 5. Cardiac troponin T

6.2.3 Safety endpoints

- 1. The number of patients with adverse events
- 2. The number of patients with serious adverse events, including
 - a. Death
 - b. Infections
 - c. Any allograft rejection
 - d. Treated allograft rejection
 - e. Renal events (sustained eGFR < 15 ml/min/1.73m², renal replacement therapy or kidney transplant)
 - f. Cardiovascular event (defined as percutaneous coronary intervention, myocardial infarction, or stroke.
- 3. The number of major clinical adverse events, defined as death, myocardial infarction, percutaneous coronary intervention/ coronary bypass surgery, cerebral stroke, cancer, or end-stage renal disease (exploratory endpoint)

6.2.4 Endpoints planned for later substudies

The following endpoints will be analysed and reported in later substudies:

- · Cardiac allograft vasculopathy at 12 months
- Inflammation biomarkers
- HDL and total cholesterol
- Quality of life assessed by the SF-36 and 5D-EuroQoL questionnaires, and the Beck's Depression Inventory

Table: Summary of objectives and endpoints for the main publication of EVOLVD

[figure not shown]
Primary objective	Primary endpoint	Data type	Method of analysis*
To evaluate the effect of the treatment on cardiac allograft vasculopathy	Maximal intimal thickness at 12 months	Continuous	ANCOVA, with adjustment for baseline values
	Secondary endpoints		
	Percent atheroma volume at 12 months	Continuous	ANCOVA, with adjustment for baseline values
	Cardiac allograft vasculopathy at 12 months	Continuous	ANCOVA, with adjustment for baseline values
Secondary objectives			
To assess the impact of treatment on cholesterol levels	LDL cholesterol at 12 months	Continuous	Linear mixed model, based on measurements at baseline, 1, 2, 3, 6, 9, and 12 months
To assess the impact of treatment on renal function	Estimated glomerular filtration rate at 12 months	Continuous	Linear mixed model, based on measurements at baseline, 1, 2, 3, 6, 9, and 12 months
To assess the impact of treatment on cardiac function	Cardiac troponin T at 12 months	Continuous	Linear mixed model, based on measurements at baseline, 1, 2, 3, 6, 9, and 12 months
	N-terminal pro-B-type natriuretic peptide at 12 months	Continuous	Linear mixed model, based on measurements at baseline, 1, 2, 3, 6, 9, and 12 months
Safety objectives	Safety/exploratory endpoints		
To assess the impact of treatment on rejections	The number of allograft rejections over 13 months' follow-up	Categorical	Descriptives
To assess the impact of treatment on safety and tolerability	The number and type of adverse events over 13 months' follow-up	Categorical	Descriptives
	The number of major clinical adverse events (death, myocardial infarction, percutaneous coronary intervention/ coronary bypass surgery, cerebral stroke, cancer, end-stage renal disease) over 12 months' follow-up	Categorical	Descriptives

7 Study Methods

7.1 General Study Design and Plan

This is a phase II, multi-centre, randomised, placebo controlled, double blind, parallel group trial. The trial is conducted at the six Nordic transplant centres in Aarhus, Copenhagen, Helsinki, Gothenburg, Lund, and Oslo. Eligible patients are randomised 1:1 and allocated to subcutaneous evolocumab or matching placebo at baseline, after providing written informed consent and performing baseline exams. The patients start treatment with 420 mg evolocumab/placebo immediately after randomisation. The study is designed to show superiority regarding the primary endpoint in patients assigned to active treatment versus patients allocated to the placebo arm.

7.1.1 Treatment Duration

12 months

7.1.2 Follow-up

13 months (including treatment duration)

7.1.3 Randomisation and treatment allocation

Treatment is allocated according to a computer based balanced, permuted block randomisation (in a 1:1: ratio for the two study arms). Treatment allocation is performed online on a password-protected platform designed for study purposes (Viedoc™) once eligibility has been confirmed, the informed consent has been signed and baseline assessments have been performed. Randomisation is stratified by centre.

7.1.4 Blinding

The study participants (patients) and all study personnel, including investigators, personnel assessing outcomes, study nurses, data analysts and treating physicians and nurses, will be blinded to study drug allocation.

7.1.5 Trial procedures

Study phases	Pre- treatment		Treatment (months)						Follow-up	
			Baseline	1	2	3	6	9	12	13 months
Eligibility	х									
Consent	х									
Vital signs	х		(x)	x	x	х	x	х	х	
Physical exam	х	₽.	(x)			х			x	
Study drug administration		anc	X	х	x	x	x	x		
Coronary angiography with		Randomisation	х						x	
IVUS		nis:								
Echocardiography		atic	х						х	
Blood samples		š	Х	X	х	х	х	х	х	
Quality of life			х						х	
Clinical events			х	x	x	x	x	×	×	x
Safety	х		(x)	х	x	х	x	x	х	x
Microcirculation (optional)			х						x	

7.1 Number of patients

We aim to enrol 130 patients in this trial.

7.2 Inclusion criteria

Patients will be screened for eligibility during routine follow-up 4-8 weeks after heart transplantation.

All the following conditions must apply prior to administering the investigational medicinal product:

- Heart transplant recipient within the last 4 8 weeks.
- Age between 18 and 70 years.
- Informed consent obtained and documented according to Good Clinical Practice (GCP), and national/regional regulations.
- · No contraindications to coronary angiography with intravascular ultrasound
- Estimated glomerular filtration rate > 20 ml/min/1.73 m2 as assessed by the MDRD formula.¹

7.3 Exclusion criteria

Patients will be excluded from the study if they meet any of the following criteria:

- Decompensated liver disease (Child-Pugh class C)
- Severe renal failure, i.e. eGFR < 20 ml/min/1.73 m2 or on renal replacement therapy
- Ongoing rejections or infections*
- Known sensitivity or intolerance to evolocumab or any of the excipients of Repatha®
- Prior use of PCSK9 inhibition treatment
- Indication for treatment with PCSK9 inhibitor
- Alcohol or drug abuse within 3 months of informed consent that would interfere with trial
 participation or any ongoing condition leading to decreased compliance with study
 procedures or study drug intake

- Participation in another clinical trial involving an investigational drug and/or follow-up within 30 days prior to enrolment.
- Pregnancy
- The subject is a nursing woman
- Female subject who has either (1) not used at least one highly effective method of birth control for at least 1 month prior to screening or (2) is not willing to use such a method during treatment and for an additional 15 weeks after the end of treatment, unless the subject is sterilised or postmenopausal

7.4 Randomisation and Blinding

The Research Support Unit at Oslo University Hospital generated a balanced, permuted, variable block size randomisation list (in a 1:1: ratio for the two study arms). We used a computerised randomisation procedure for treatment allocation. Random treatment allocation was executed on the online, password-protected platform designed for study purposes (Viedoc™) once eligibility had been confirmed and the informed consent had been signed. Study nurses who were blinded to study drug content administered identical-looking drug packages to the patients according to the randomisation number generated for each patient. The investigator or study nurse who randomised the patient was responsible for presenting the randomisation number to the designated unblinded personnel dispensing the study drug and registering the corresponding kit-number in the eCRF. The study drug was not administered/ dispensed to the patient before the kit number had been entered in the eCRF and no error message was generated. The study participants (patients) and all study personnel, including investigators, personnel assessing outcomes, study nurses, data analysts and treating physicians and nurses, are blinded to allocation to study drug.

[figure not shown]
7.5 Study Variables

7.5.1 Primary endpoint:

The primary endpoint, the maximal intracoronary intima thickness, is measured as the largest distance from the intimal leading edge to the external elastic membrane on matched slices of the same coronary vessel (Figure 1). All intracoronary ultrasound analyses will be conducted after trial closure at a core laboratory (Oslo University Hospital, Rikshospitalet, Oslo, Norway) by personnel blinded to patient treatment. Precise matching of the IVUS recordings at baseline and at 12 months will be performed and contour detection of both the lumen and external elastic membrane will be performed at approximately 1 mm intervals using validated software (QIVUS, v.3.0, Medis medical imaging systems, Leiden, the Netherlands). Borders will be reviewed by two independent operators according to the guidelines for acquisition and analysis of intravascular ultrasound (IVUS) images by the American College of Cardiology and European Society of Cardiology.

Figure 1

[figure not shown]

Illustration of single slice of coronary ultrasound images. Multiple slices are recorded at constant intervals along a coronary vessel and matched (baseline/follow-up) for direct comparison. The primary endpoint of the trial is the maximal intima thickness, measured from the external elastic membrane (EMM) to the luminal border. The percent atheroma volume is the percentage of the intima area (EMM area – lumen area) that contains lipids (different echogenicity than the healthy intimal area) across the entire matched segment of the coronary artery. (E From Stephen J. Nicholls et al, Relationship Between Cardiovascular Risk Factors and Atherosclerotic Disease Burden Measured by Intravascular Ultrasound. JACC 2006:47;1967-75.

7.5.2 Secondary endpoints:

The secondary endpoints "percent atheroma volume" and "cardiac allograft vasculopathy" will be analysed on matched sections of the IVUS images of the coronary vessel with contour detection of the lumen and external elastic membrane for each mm. "Percent atheroma volume" expresses the summation of atheroma areas in proportion to the area between the lumen and the external elastic membrane (in percent) (Figure). "Cardiac allograft vasculopathy" is defined as the extent to which the mean maximal intimal thickness is ≥0.5 mm over the entire matched segment.

8 Sample Size

This trial is designed to assess the effect of evolocumab on intima thickness as measured by coronary IVUS. The sample size of the present study is based calculations relating to the primary outcome, the change in maximal intima thickness from baseline to one year. In the SCHEDULE trial, we observed an increase in the maximal intima thickness of 0.08 (SD 0.12) mm in the placebo group, whereas the corresponding increase was 0.03 (SD 0.06) mm in the everolimus arm.² Intensive cholesterol reduction has been shown to actually reverse the atherosclerotic volume in previous trials.³,⁴ We therefore hope to achieve a 0.05 mm between-group difference in the change in the intima thickness in the EVOLVD trial. With an estimated 0.09 mm standard deviation, we will require 51 patients in each arm with a power of 80%, at a two-sided alpha level of 5%. To increase the chances of reaching the primary and secondary outcomes, and to compensate for uncertainties in

this calculation, we will aim for 120 patients to complete the one-year follow-up. To allow for a dropout rate of 5 - 10%, we plan to include 130 patients.

9 General Considerations

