1.6 Rationale for study endpoint

The ultimate endpoint for risk-reducing drugs is all-cause mortality. Currently, the one-year survival in heart transplant recipients is almost 90 %. Thus, for adequate power, an outcome-driven trial would require hundreds, possibly thousands of patients to show a difference between treatment

groups. With a mere 5000 patients receiving a cardiac allograft each year world-wide, designing a trial with coronary outcomes or mortality as primary endpoints simply is not feasible. Intima thickness as measured by IVUS is an established surrogate endpoint for coronary heart disease. Trials have shown that aggressive lipid-lowering treatment can alleviate, or even reverse, the atherosclerotic burden in patients with coronary heart disease.³⁸⁻⁴⁰ In these trials, the primary efficacy endpoint has been the percentage atheroma volume, defined as

 $\frac{\text{the area enclosed by the external elastic membrane- the luminal area}}{\text{the area enclosed by the external elastic membrane}} * 100.40$

On the other hand, in heart transplant recipients, it is the maximal coronary intima thickness that has been shown to be associated with outcome.^{41, 42} These measures are closely correlated. Our own data show that IVUS measurements are reproducible and that the repeated measure variability in intima thickness is low.^{21, 37} Furthermore, the measurement is not associated with significant risk on top of the risk associated with coronary angiography,³⁵ which is performed on a regular basis in heart transplant recipients.

2 Study objectives and related endpoints

The main goal of this study is to evaluate the effect of evolocumab administered subcutaneously every month for one year on the development of cardiac allograft vasculopathy in cardiac allograft recipients.

Secondary objectives are to assess the impact of treatment on: i) cholesterol levels, ii) renal function, iii) inflammation, iv) cardiac function as assessed by biomarkers and echocardiography, v) quality of life, vi) the number of allograft rejections, and (vii) safety and tolerability. As an exploratory endpoint, we will assess the impact of treatment on the number of major clinical events (death, myocardial infarction, percutaneous coronary intervention/coronary bypass surgery, cerebral stroke, cancer, and end stage renal disease).

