10.1 Determination of sample size

This trial is designed to assess the effect of evolocumab on intima thickness as measured by coronary IVUS. The sample size of the present study is based calculations relating to the primary outcome, the change in maximal intima thickness from baseline to one year. In the SCHEDULE trial, we observed an increase in the maximal intima thickness of 0.08 +/- 0.12 mm in the placebo group, whereas the corresponding increase was 0.03 +/- 0.06 mm in the everolimus arm.²¹ Intensive cholesterol reduction has been shown to actually reverse the atherosclerotic volume in previous trials. We therefore hope to achieve a 0.05 mm between-group difference in the change in the intima thickness in the EVOLVD trial. With an estimated 0.09 mm standard deviation, we will require 51 patients in each arm with a power of 80%, at a two sided alpha level of 5%. To increase the chances of reaching the primary and secondary outcomes, and to compensate for uncertainties in this calculation, we will ensure that 120 patients complete the one-year follow-up. To allow for a dropout rate of 5 - 10% we aim to include 130 patients.

In the SCHEDULE trial, the mean increase in the percent atheroma volume was 1.3 ± 2.3 percentage points in the everolimus arm versus 4.2 ± 5.0 percentage points in the cyclosporine group. Provided that evolocumab can produce a similar reduction in the progression of the atheroma volume, with an estimated standard deviation of 3.7 percentage points, we will need just 26 patients in each arm to detect a between-group difference in the important secondary outcome, the change in percent atheroma volume, with an α of 5 % and a power of 0.8.

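### As the SAP words it, percent atheroma volume is a share of the intima and not of the vessel area, so it does not measure plaque burden

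*SAP*

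**What the plan says.** **PAV in the SAP.** Section 6.2.2 lists PAV first among the secondary endpoints. Section 7.5.2 says that it "expresses the summation of atheroma areas in proportion to the area between the lumen and the external elastic membrane (in percent". The Figure 1 legend in 7.5.1 is more specific: "The percent atheroma volume is the percentage of the intima area (EMM area – lumen area) that contains lipids", with a parenthesis describing lipid as having "different echogenicity than the healthy intimal area" (EMM there stands for the external elastic membrane, EEM). The core laboratory work planned in 7.5.2 is "contour detection of the lumen and external elastic membrane for each mm"; no lipid or atheroma contour is mentioned.

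**PAV in the protocol.** Section 1.6 introduces the measure through earlier lipid-lowering trials: "In these trials, the primary efficacy endpoint has been the percentage atheroma volume, defined as", followed by a fraction whose numerator is "the area enclosed by the external elastic membrane- the luminal area" and whose denominator is the area enclosed by the EEM, times 100. Of PAV and maximal intimal thickness the section says "These measures are closely correlated". Section 2.2 lists PAV as a secondary endpoint without restating a formula. Section 10.1 plans for it in these terms: "Provided that evolocumab can produce a similar reduction in the progression of the atheroma volume". Section 7.1.1 does not list PAV among the secondary IVUS variables; it names normalised total atheroma volume instead.

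**Cardiac allograft vasculopathy (CAV).** Protocol 7.1.1 calls it an incidence, at a mean maximal intimal thickness of at least 0.5 mm. SAP 7.5.2 words it as an extent, and the summary table after SAP 6.2.4 and SAP 11.2 treat it as continuous, with ANCOVA. SAP 6.2.2 omits it and 6.2.4 defers it to later substudies, but the table, which is headed as covering the main publication, includes it.

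**The concern.** A burden measure asks how much of the vessel cross-section is plaque. A share of the intima asks what the plaque consists of. These are different quantities, and a treatment can move them in different directions. SAP 7.5.2 and the legend both take the area between lumen and EEM as denominator, so this is not one loose phrase that the other corrects.

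At stake is whether the leading secondary result can do what it is there for. SAP 11.1 uses secondary results as support for the primary endpoint, and protocol 1.6 and 10.1 rely on PAV as a measure of burden that tracks intimal thickness and progresses over a year. A composition measure, or a constant, cannot give that support. If the core laboratory instead computes the burden formula, the reported variable departs from the written plan, and that has to be explained after unblinding when it could have been settled before.

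**Working it through.** **1. The plan's own figures.** Normal approximation, two-sided 5%, 80% power, 1:1 allocation: n per arm = 2 × (1.960 + 0.842)² × SD²/difference².

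- Primary endpoint (protocol 10.1: SD 0.09 mm, difference 0.05 mm): 2 × 2.802² × 0.09²/0.05² = 50.9, so 51 per arm, as stated.
- PAV (protocol 10.1: SD 3.7 points, difference 4.2 − 1.3 = 2.9 points): 2 × 2.802² × 3.7²/2.9² = 25.6, so 26 per arm, as stated.

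Both reproduce. No corresponding figure can be computed for the SAP's wording, because the documents give no mean or SD for a share of the intima.

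**2. The definitions side by side.**

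| Source | Numerator | Denominator |
|---|---|---|
| Protocol 1.6 | EEM area − lumen area | EEM area |
| SAP 7.5.2 | sum of atheroma areas | EEM area − lumen area |
| SAP Figure 1 legend | lipid-containing area | EEM area − lumen area |

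**3. If atheroma area means EEM minus lumen.** This is the only area that the planned contours yield. Numerator and denominator are then identical. With assumed areas (EEM 15 mm²; lumen 12.0 mm² at baseline and 11.4 mm² at 12 months), the SAP ratio is 3.0/3.0 = 100% and then 3.6/3.6 = 100%. In the SAP 11.2 model every outcome and every baseline value would be 100, so no treatment difference could appear.

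**4. If it means lipid-containing area, as in the legend.** Same assumed areas.

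- Protocol 1.6: (15 − 12.0)/15 = 20.0%; (15 − 11.4)/15 = 24.0%; change +4.0 points. Plaque area grows from 3.0 to 3.6 mm², that is by 20%.
- SAP: with baseline lipid share s and lipid growth g, the share at 12 months is s(1 + g)/1.2. Assume s = 30% (0.90 mm²):

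| Lipid growth | Lipid area at 12 months | Share at 12 months | Change in points |
|---|---|---|---|
| 0% | 0.90 mm² | 25.0% | −5.0 |
| 10% | 0.99 mm² | 27.5% | −2.5 |
| 20% | 1.08 mm² | 30.0% | 0 |
| 30% | 1.17 mm² | 32.5% | +2.5 |
| 40% | 1.26 mm² | 35.0% | +5.0 |

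Over the same growth range, a baseline share of 10% gives −1.7 to +1.7 points and one of 50% gives −8.3 to +8.3. Burden rises by 4.0 points in every case. The share rises only if lipid grows proportionally faster than the plaque.

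The areas, shares and growth rates are all assumed. The example shows that the measures can diverge; it does not estimate anything for this trial.

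**The case against.** The strongest reply is that this is loose wording about an ordinary burden measure. Much points that way: only lumen and EEM contours are planned, in validated software and under published IVUS guidelines; the source cited under Figure 1 has disease burden in its title; and protocol 10.1 plans on mean PAV changes of 1.3 and 4.2 points, which a constant of 100% could not show. I accept this as the likely explanation. It makes the correction easy but does not remove the need for it, since nothing in the SAP overrides the written definition.

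Two limits on the evidence also stand. Figure 1 itself is not available, so the point rests on its legend and on 7.5.2. Protocol 1.6 gives its formula for earlier trials and not expressly for this one, although no other formula appears.

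A reader might infer that the trial will report a lipid share, or that its PAV result will come out with the wrong sign. The documents do not support that. Movement against burden is possible only under the legend's reading; under the other reading the variable cannot move at all.

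A reader might also infer that the SAP leaves the analyst to choose the type of variable and model for CAV. It does not: 7.5.2, the table and 11.2 consistently treat CAV as graded, and the table and 11.2 specify ANCOVA. What remains is a missing formula and unit, and a difference from the protocol's incidence. On reporting place, 6.2.2 and 6.2.4 agree with each other, and the table row is the outlier.

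**Conclusion.** The PAV definition in the SAP is wrong as written and should be corrected. Neither available reading gives the plaque burden on which protocol 1.6 and 10.1 rely: one is plaque composition with no stated method beyond a remark on echogenicity, the other is a constant. The mismatch itself is certain from the text; the intention behind it is not, and a slip is more probable than a deliberate change of variable.

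The reach is limited. Only secondary endpoints are affected, and SAP 11.1 treats their results as supportive or exploratory. The primary endpoint and its 51 per arm stand. So does the 26 per arm for PAV, on the assumption that the planning figures are on the scale of protocol 1.6.

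The missing PAV entry in protocol 7.1.1, the missing formula for CAV and its double listing are minor and would not carry the point alone.

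**What to change.** Before database lock:

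1. In SAP 7.5.2 define PAV = Σ(EEM area − lumen area)/Σ(EEM area) × 100 over the matched slices, and take the lipid wording out of the Figure 1 legend. Protocol 1.6 gives no rule for combining slices, so the sums need to be written out. If a lipid share is really intended, give it another name and state how the lipid area is measured.
2. State whether normalised total atheroma volume (protocol 7.1.1) is kept as a separate variable or dropped.
3. For CAV, choose one of two routes. Either give the formula and unit of the graded measure and keep ANCOVA; or define it as yes/no at 12 months (mean maximal intimal thickness ≥0.5 mm), say how patients already at or above 0.5 mm at baseline are handled, and use a binary-outcome model adjusted for baseline mean maximal intimal thickness, with 11.2 and the table changed to match.
4. Bring the CAV row of the main-publication table into line with 6.2.2 and 6.2.4, or the reverse.

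The cost is SAP wording. Protocol 10.4 permits changes to the plan up to the day of database lock. The planned contours already give EEM area, lumen area and maximal thickness per slice, so the burden formula and the 0.5 mm threshold need no new measurement.
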